#### 10.4. Statistical rules for trial early trial termination / Interim analysis

An interim analysis will be performed after observing 70% of the number of expected events (i.e. 138 events). Stopping rules using the spending function approach of Lan and DeMets ([Lan, 1983](#)) with O'Brien-Fleming type spending function ([O'Brian, 1979](#)) will be followed to conclude at each sequential analysis.

The interim analysis boundary values are determined using the software EASTR.

Nominal p values for overall type I error of 0.05 Lan-DeMets boundaries are:

- Efficacy interim analysis (138 events, i.e. 70% expected events): p-value to reject  $H_0 \leq 0.015$  (equivalent to the stopping boundaries Z-Scale:  $\pm 2.437$ )
- Final analysis (197 events, i.e. 100% expected events): p-value to reject  $H_0 \leq 0.045$  (equivalent to the stopping boundaries Z-Scale:  $\pm 2.0$ )

The results of the interim analyses will be given only to the IDMC members.

These values are given as an indication and will be recalculated according to the actual number of events at the time of the intermediate and final analysis.

## 11. OVERSIGHT COMMITTEES

### 11.1. Independent data monitoring committee

An IDMC, with expertise and experience in the pathology, and without direct involvement in the conduct of the trial, will be set up specifically to guarantee:

- Effective protection of patients.
- Insure the ethical conduct of the trial.
- Benefit/risk ratio of the trial.
- Ensure the independent review of the scientific results during and at the end of the trial.

The IDMC will be composed of at least 3 expert members (2 clinicians and 1 statistician). IDMC members must have no financial interest in the outcome of the trial and be independent from the Investigators, Funding bodies, Sponsor, Steering committee and any other institutions involved in the trial.

The IDMC committee shall meet in any of the following cases:

- In the event of an alert issued by the pharmacovigilance department,
- In case of concerns from the Steering Committee for the analysis or interpretation of the efficacy results according to the hypotheses defined in the protocol,
- In the event of an unsatisfactory enrolment rate,

- To review the results of predefined interim analyses

Once formed and during the first meeting, the committee shall define the schedule of meetings until the end of the trial. This schedule can be modified depending on safety signals.

The IDMC will perform a blinded review of accumulated data regarding overall safety and efficacy of the study treatment including the results of scheduled analyses, collected safety reports prepared by the Sponsor as well as published data and information provided by the IP license holder concerning concurrent studies. Data presented to IDMC are strictly confidential.

The IDMC will provide recommendations regarding continued recruitment or termination of enrolment in each cohort, or if new cohorts/indications should be considered as well as any modifications of protocol design which might be necessary.

The IDMC may recommend the early termination of the trial if one of the following conditions is met:

- The interim analyses are in favour of stopping the trial for futility or for efficacy.
- An unacceptable level of toxicity is reported.
- All available data from the trial or any other source of information are sufficiently convincing to influence the therapeutic practices of the majority of clinicians.

The IDMC has only a consultative role; it will inform the Sponsor and Steering Committee who will decide whether the IDMC recommendation will be followed.

The roles and responsibilities of the IDMC are further detailed in the IDMC Charter.

## 11.2. Steering Executive Committee

A Steering Committee has been implemented for this trial. The Steering Committee will meet on an annual basis. Additional meetings may be set, as required.

The Steering Committee is composed of:

- The trial Coordinating Investigator
- The trial Biostatistician
- The Coordinating Investigator of the PEACE 6 programme
- Project Manager (or delegate)
- Other participants as required depending the meeting agenda

The Steering Committee will review the accumulated data regarding overall safety and efficacy of the study treatment, including the results of programmed analyses, collated safety reports prepared by the Sponsor, as well as published data and information provided by the IP license holder concerning concurrent studies. The Steering Committee will also review, or may request, recommendations made by the IDMC. The Steering Committee, based on this information, will assist the Sponsor in resolving issues and/or questions encountered during the conduct of the trial and will make recommendations regarding modifications to the protocol.

Recommendations made by the steering committee will be implemented as soon as possible following Sponsor approval. Any recommendations which would result in substantial modifications to the conduct of the study or amendment of the protocol design must obtain approval from the applicable Health Authorities and local ethics committees prior to implementation in each participating country.

The roles and responsibilities of the Steering Committee are further detailed in the Steering Committee Charter.

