## 10. DESCRIPTION OF STATISTICAL METHODS

The statistician will produce an initial statistical analysis plan before the inclusion of the first patient (version n°1). This document will be validated by the Steering Committee. The SAP may be revised during the course of the trial in case of substantial modification of the protocol or following recommendations of the Independent Data Monitoring Committee (IDMC). Any revision of the SAP will be validated by the Steering Committee.

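### Section 11.2 lets the Steering Committee review accumulating efficacy data and programmed analyses with no blinded or pooled limit, in conflict with the rule in 10.4 that interim results go only to the IDMC

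*Protocol*

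**What the plan says.** Section 10.4, and the statistical part of the protocol summary in the same words, state: "The results of the interim analyses will be given only to the IDMC members". Section 11.1 adds that what the IDMC is shown is confidential, and requires IDMC members to be independent of the Steering Committee.

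Section 11.2 describes the Steering Committee differently: "The Steering Committee will review the accumulated data regarding overall safety and efficacy of the study treatment, including the results of programmed analyses". On the basis of this information the committee "will assist the Sponsor in resolving issues and/or questions encountered during the conduct of the trial and will make recommendations regarding modifications to the protocol". It meets every year. Its members are "The trial Coordinating Investigator", "The trial Biostatistician", the coordinating investigator of the PEACE 6 programme, the project manager or a delegate, and others as needed.

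Two other places bear on this:

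- Section 11.1 lists among the triggers for an IDMC meeting: "In case of concerns from the Steering Committee for the analysis or interpretation of the efficacy results".
- Section 10 gives the committee a say over the analysis: "Any revision of the SAP will be validated by the Steering Committee".

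**The concern.** The trial is double-blind, and its primary endpoint, rPFS, rests on progression as called by investigators (3.1, 3.2.1). Central review is only a sensitivity analysis, and is done only if the primary result is positive (6.1.1, 10.3.2). It therefore does not replace confidentiality of the interim result.

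The committee named in 11.2 influences the course of the trial. It validates SAP revisions, recommends protocol amendments and, with the sponsor, decides whether to follow the IDMC (11.1). The sample size may also be adjusted for drop-out while the trial runs (10.1). If those who take part in such decisions could have seen the interim comparison, nobody could show afterwards that a change was made independently of it. What is at stake is the credibility of conduct and of later SAP or protocol changes.

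**Working it through.** **1. The texts side by side.**

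| Question | 10.4 and summary | 11.2 |
|---|---|---|
| Who sees interim results? | IDMC members only | Steering Committee reviews results of programmed analyses |
| When? | At the interim | Yearly meetings, for issues arising during conduct |
| Limit to blinded or pooled data? | Not needed | None stated |

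Section 11.1 describes the IDMC's review in nearly the same terms as 11.2 but calls it blinded. That word is missing from 11.2. Section 11.2 also mentions IDMC recommendations separately, so its programmed analyses are not simply another name for those recommendations.

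**2. Which programmed efficacy analysis could be meant during the trial?** Section 10.4 schedules one interim, at 138 events (70%), and the rPFS analysis at 197. Before the rPFS readout the interim is the only candidate.

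**3. The plan's design figures reproduce.** Inputs from 10.1 and 10.4: HR 0.65, two-sided 5%, power 85%, 138 and 197 events, 1:1 allocation.

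- Required events are 194 by Schoenfeld and 200 by Freedman; the plan has 197.
- Lan-DeMets spending of O'Brien-Fleming type at 138/197 = 0.7005 gives boundaries of 2.437 (p = 0.0148) and 2.000 (p = 0.0455), with power 0.851. No figure in the plan is in dispute.
- HR at the boundary = exp(−2z/√D). Interim: exp(−2 × 2.437/√138) = 0.66. Final: exp(−2 × 2.0/√197) = 0.75.

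**4. How much of the trial remains at the interim.** Events: 197 − 138 = 59, and 59/197 = 30%.

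For calendar time, use the accrual table in 10.1 (18, 50 and 53 patients in the first three years, then 179 over 24 months). The control hazard is ln 2/12 = 0.0578 per month, the experimental hazard 0.65 × 0.0578 = 0.0375, and the drop-out hazard δ = 0.014. A patient who entered at month u has had an event by month t with probability λ/(λ+δ) × [1 − exp(−(λ+δ)(t−u))]. Summing over entries gives 138 expected events at month 58.0 and 197 at month 75.2, close to the plan's 75. At month 58.0, 121 + (179/24) × 22.0 ≈ 285 of the 300 patients are randomised.

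**5. How informative the interim would be (illustration only).** At HR 0.65 the mean interim Z is 0.4308 × √138/2 = 2.530. The probability of crossing 2.437 is 1 − Φ(2.437 − 2.530) = 0.537, so the trial continues with probability 46%. With I₁ = 138/4 = 34.5, I₂ = 197/4 = 49.25 and θ = 0.4308, the probability of final success given interim z is

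1 − Φ{[2.0√I₂ − z√I₁ − θ(I₂ − I₁)] / √(I₂ − I₁)}.

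Over trials that continue:

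| Assumption for remaining events | 5th percentile | Median | 95th percentile |
|---|---|---|---|
| HR 0.65 | 12% | 77% | 95% |
| Observed interim trend | 0.7% | 61% | 94% |

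The mean under HR 0.65 is 68%.

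**The case against.** The strongest defence is that 11.2 never says by arm, unblinded or interim, and that the explicit rule, stated twice, is IDMC only. A specific rule can be read as limiting a general one. Programmed analyses could also mean later ones: follow-up runs for 10 years per patient, and 10.1 schedules a further analysis 10 years after the last inclusion. The Steering Committee charter, which is not available here, may narrow access. The trigger in 11.1 could refer to planned methods or pooled event rates.

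This shows that the texts can be harmonised by adding a limit, and that 11.1 is only weak support for the idea that the committee holds results by arm. It does not supply the missing limit. Section 11.2 describes review during conduct, and a charter should not have to correct the protocol.

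A reader might infer three stronger things, which the documents do not support:

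- *The people running the trial would know its result.* A success probability from 12% to 95%, with mean 68%, is informative but far from decisive: about one continuing trial in three still fails even at HR 0.65.
- *The blind would be lost.* An aggregate hazard ratio reveals no patient's allocation, progression is called by investigators across about 100 sites, and code-breaking is restricted by 3.5.
- *The 5% error rate would be indefensible.* The spending function is fixed in advance, and substantial protocol changes need authority and ethics approval (11.2). No inflation has been shown.

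**Conclusion.** The point stands as a conflict in the governance text. Sections 10.4 and 11.2 give different answers on who may see efficacy results during the trial, and 11.2 lacks the limit that would reconcile them. Applied as written, it would allow a committee that validates SAP revisions and recommends amendments to see an informative comparison with 59 of 197 events (30%) still to be assessed. That would leave trial conduct and later changes open to challenge.

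The contradiction and the 30% rest on the protocol text alone. The calendar and conditional-power figures assume exponential times, the projected accrual and the design hazards, and only illustrate the consequence. Nothing indicates that results have been or will be shared. The current version is dated December 2024 with about 115 of 300 patients enrolled. On the plan's own assumptions, month 58 from March 2022 falls about two years later, so the text can be put right before the question arises.

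**What to change.** In the next amendment:

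- **11.2:** until the final rPFS analysis or a decision to stop, limit the Steering Committee to pooled data not split by arm (recruitment, data quality, event counts, safety), external information and the IDMC's recommendation.
- **11.1, meeting trigger:** reword it so that Steering Committee concerns refer to pooled, blinded data. It need not be deleted.
- **11.1, IDMC review:** reconcile the description of this review as blinded with the efficacy boundary in 10.4, which needs a comparison between arms.
- **10.4 or 11.1:** state that interim results by arm are prepared by a statistician who is not on the Steering Committee, since the trial biostatistician is a member.
- **Charter:** align the Steering Committee charter with the new text.

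The cost is a few sentences, the charter revision and the naming of a separate statistician for the interim report. Sample size, boundaries and visit schedule do not change.

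### Section 11.2 lets the Steering Committee review accumulating efficacy and programmed-analysis results, which contradicts the rule that interim results go only to the IDMC

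*Protocol*

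**What the plan says.** **Who receives interim results.** Protocol section 10.4 states: "The results of the interim analyses will be given only to the IDMC members". The statistical part of the protocol summary repeats this. Section 11.1 adds that what the IDMC is shown is strictly confidential, and that IDMC members must be independent of the Steering Committee as well as of the sponsor and investigators.

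**What the Steering Committee reviews.** Under section 11.2 the committee will "review the accumulated data regarding overall safety and efficacy of the study treatment, including the results of programmed analyses". It does not say pooled, blinded or after the primary analysis. The committee meets every year and uses this information to help the sponsor with issues arising while the trial is conducted and to recommend protocol modifications.

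**Who sits on it.** Section 11.2 lists "The trial Coordinating Investigator", "The trial Biostatistician", "The Coordinating Investigator of the PEACE 6 programme", the project manager or a delegate, and others as the agenda requires.

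**What else it decides.** Section 10: "Any revision of the SAP will be validated by the Steering Committee". Under section 11.1 it also decides, together with the sponsor, whether an IDMC recommendation is followed. Those recommendations may include changes to the protocol design.

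**What the IDMC reviews.** Section 11.1: "The IDMC will perform a blinded review of accumulated data". The same section lets the IDMC recommend stopping for efficacy, futility or unacceptable toxicity.

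**The concern.** The trial is double-blind and placebo-controlled, with one planned efficacy look at 138 events. Keeping the interim comparison away from those who run the trial is what makes later decisions credible. Section 11.2 as worded opens that comparison to the people who can change the SAP and propose changes to the protocol.

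Several decisions still lie ahead and should be made without by-arm knowledge. Section 10 allows SAP revisions during the trial. Section 10.1 allows the sample size to be adjusted if drop-out rises. Section 10.4 provides for the boundaries to be recalculated from actual event counts. Knowledge of a trend could also affect recruitment effort, willingness to keep patients on blinded treatment, and the start of later therapy. The primary endpoint is investigator-assessed. Central review is only a sensitivity analysis, run if the primary result is positive (sections 6.1.1 and 10.3.2), so it is not a general safeguard.

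A second, smaller problem is the word blinded in section 11.1. If it means pooled, the IDMC could neither apply the boundary nor see an imbalance in harm. If it means coded arms, it could do both. The text does not say which.

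**Working it through.** **1. The access rules side by side**

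| Question | Sections 10.4, 11.1 and summary | Section 11.2 |
|---|---|---|
| Who gets interim results? | IDMC members only | Steering Committee reviews programmed-analysis results |
| Limited to blinded data? | IDMC review called blinded | No limit stated |
| When? | At the interim | During the trial; committee meets annually |

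The only efficacy analysis of rPFS that the protocol programmes before the 197-event analysis is the 138-event interim. During that period, the results of programmed analyses can therefore only mean the interim. Section 11.1 also has the IDMC meet if the Steering Committee has concerns about the analysis or interpretation of the efficacy results, which suggests that the committee is expected to see some.

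**2. Reproducing the plan's boundaries**

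Inputs (section 10.4): 138 and 197 events, overall two-sided 0.05, Lan-DeMets spending of O'Brien-Fleming type. Information fraction t = 138/197 = 0.7005. Spending 0.025 in each tail:

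- Interim: Z = 2.437, two-sided p = 0.0148 (protocol: 2.437 and 0.015).
- Final: Z = 2.000, two-sided p = 0.0455 (protocol: 2.0 and 0.045).

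The boundaries are correct. The point is about access, not about these values.

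**3. When the interim falls**

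Inputs (section 10.1):

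- accrual of 18, 50 and 53 patients in years 1, 2 and 3, then 179 over 24 months (7.46 per month);
- control median 12 months; HR 0.65, so experimental median 12/0.65 = 18.46 months;
- exponential event times; drop-out hazard 0.014, taken as per month because the protocol gives no unit.

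Hazards: ln 2/12 = 0.0578 and ln 2/18.46 = 0.0375 per month. With event hazard λ and drop-out hazard δ, a patient entering at month u has had an event by month T with probability λ/(λ+δ) × [1 − exp(−(λ+δ)(T−u))]. Integrating over the accrual table, half of each period's patients in each arm:

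- Month 75: 107.8 + 88.9 = 196.7 events. This reproduces the protocol's 197 events at 75 months and supports the per-month reading.
- Month 58: 77.2 + 60.6 = 137.9 events. The interim therefore falls at about month 58.
- Randomised by month 58: 300 − 2 × 7.46 = about 285.

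**4. What a result at the boundary would look like**

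With 1:1 allocation the standard error of the log HR is about 2/√138. The boundary HR is exp(−2 × 2.437/√138) = 0.66.

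**5. What would remain to be collected**

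197 − 138 = 59 events; 59/197 = 30%. The last 15 or so randomisations (300 − 285) and the later follow-up for clinical progression-free survival and overall survival would also come after the interim.

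**The case against.** The strongest defence is that section 10.4 is the specific rule, uses the word only, and is repeated in the summary, while section 11.2 is a general remit. Programmed analyses is undefined and could mean the primary and 10-year analyses of a 15-year trial. Both committees' duties are referred to charters that are not available here and may restrict access. This makes a wording conflict more likely than an intention to unblind. It does not remove the conflict: section 11.2 states no such limit, and its review is tied to decisions made during the trial.

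Four stronger readings are tempting, and the protocol does not support them.

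- **A reader might infer that progression reads would no longer be blind.** An aggregate hazard ratio reveals no patient's allocation. Treatment is placebo-controlled, code-breaking is restricted (section 3.5), the summary plans 100 sites, and section 11.2 names only two investigator roles.
- **A reader might infer that the type I error is lost.** Nothing here quantifies an inflation. The exposure is to biased decisions if access occurs.
- **A reader might infer that the IDMC cannot use its boundary.** The boundary is two-sided (±2.437), so coded arms allow the test and would show an imbalance in harm. Section 11.1 also has the IDMC review predefined interim analyses, which presupposes comparative results. The term is ambiguous rather than disabling.
- **A reader might infer that the committee approves protocol changes.** It recommends them. The sponsor approves, and substantial changes need authority and ethics approval. Its authority over SAP revisions is explicit.

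**Conclusion.** The contradiction stands and should be resolved before the interim analysis. As written, section 11.2 gives the Steering Committee what section 10.4 and the summary reserve for the IDMC, and that committee has authority over SAP revisions and a say in protocol changes and in acting on IDMC advice.

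The size is conditional. Only if section 11.2 is followed at the interim and the trial then continues would 30% of the primary events accrue after trial leadership knew the comparison. The month-58 timing rests on the protocol's projected accrual, its assumed medians, exponential event times and a monthly drop-out hazard. The 59-event count rests only on the two planned event totals. What is at risk is the independence of SAP and protocol decisions, equipoise and trial conduct.

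The wording of the IDMC's review in section 11.1 is a separate and lesser matter that needs clarification.

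**What to change.** **Section 11.2.** State that until the primary analysis, or until the IDMC recommends stopping, the Steering Committee receives only pooled, blinded safety and conduct data and the IDMC's recommendations, with no by-arm efficacy data and no interim results. If the IDMC recommends stopping, release only what is needed for that decision. This exception is necessary because section 11.1 makes the committee, with the sponsor, decide whether to follow the recommendation.

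**Section 11.1.** Replace the blinded review with a closed-session review of by-arm data. Arms may be coded, provided the code is available to the IDMC. Name as author of the report a statistician who is not on the Steering Committee and is independent of trial conduct. Staff of the sponsor's own data centre would not by that fact alone be independent, since section 12.1 places the database under the sponsor's data department.

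**Section 10.** State that SAP revisions are made without by-arm data.

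**Cost.** A few sentences in the protocol and matching lines in the two charters. There is no change to sample size, boundaries or data collection. With about 115 of 300 patients enrolled at this amendment there is time, whereas a disclosure of interim results could not be undone.

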## 12. QUALITY ASSURANCE

### 12.1. Data collection

Data necessary for patient randomisation and treatment allocation/management will be entered into the trial IWRS, hosted by EURAXI ([name]).

All data necessary for the research must be entered into the trial eCRFs in a timely manner. eCRFs will be completed by the principal investigator and other staff members duly designated. The data entered must be accurate and complete.

The trial database will be hosted by AZ Network ([name]) under the responsibility of the Unicancer Data Department.

Database management will be performed by the Unicancer Data Center (Institut du Cancer Montpellier (ICM) – Val d'Aurelle, Unité de Biométrie – CTD INCa, [name]) under the responsibility of [name].

The database will be accessed via an eCRF developed using the CSOnline module of Ennov Clinical® software. In case of technical problem with the eCRF, the investigator may refer to the specific operating procedure of the eCRF or directly contact:

from Monday to Friday 9 am-5 pm

email: [[contact]](mailto:[contact])

[contact]

[contact]

The access code (login) and passwords to access the eCRF (via the website - <https://ecrf.icm.unicancer.fr/CSOnline>) will be generated automatically by CSOnline and sent directly to the users registered email account.

A password non-disclosure certificate will be signed by the principal investigator of each site engaging his/her responsibility regarding the confidentiality of the access codes for all users of the eCRF at their site.

Trial data will be entered into the eCRF by the principal investigator, or by designated staff members of each site, and will be controlled and validated according to the standard procedures (including those built-in to the software and the sponsor's quality assurance procedures). All access to the eCRF and changes made to the data are recorded by the software (audit trail). At the end of the trial and once all the eCRF data are validated, the investigator will login to the eCRF to sign all the pages to validate the data entered for each patient.

The sponsor will create and send an electronic copy (PDF file) of each patient's CRF to the corresponding investigator. This pdf file must be printed and signed by the investigator, and then archived at the investigator's site.

